1.2 Trial Diagram

Figure 1: Trial Diagram

Abbreviations: SC, subcutaneously; WK, week.

1.3 Schedule of Assessments

The screening evaluation will only be performed after the participant has agreed to participate and has signed and dated the ICF. No treatment or trial-related procedures will be initiated before the informed consent is signed. The Day 1 visit must be performed, at the latest, 30 days after the screening visit.

The screening evaluation will be performed according to the inclusion and exclusion criteria. If the participant fulfills all inclusion criteria and no exclusion criteria, he or she may be enrolled in the trial.

Table 1 provides a description of the procedures to be performed at each visit.

Unless specified otherwise, the trial assessments scheduled on Day 1 must be performed before the IP administration. The recommended order for performing the trial assessments is as follows (applicable to all visits), except for collection of blood samples for analysis of serum daxdilimab ADA and PK samples, which must be performed prior to IP administration at the visits specified in Table 1 (refer to footnotes):

- Investigator assessments
- Vital signs
- 12-lead ECG
- Medical photographs
- Blood draw

Table 1: Schedule of Assessments

Window (days) X <																
Informed consentXXXXXXXXXDemographicsXXXXXXXXXXXMedical and surgical historyXXXXXXXXXXXXInclusion/exclusion criteriaXXXXXXXXXXXXXHeightXXXXXXXXXXXXXXBody weightXXXXXXXXXXXXXXXPhysical examination ² XXX <t< th="">Procedure																</t<>	Procedure															
$\begin{array}{c c c c c c c c c c c c c c c c c c c $	Window (days)															
Medical and surgical historyXXXImage: constraint of the system of the syste	Informed consent	Х														
$ \begin{array}{c c c c c c c c c c c c c c c c c c c $	Demographics	Х														
HeightXX Medical and surgical history	Х	X		Medical and surgical history	Х	X													
Body weightXXXXXXXXXXXXPhysical examination ² XXX <t< td="">Inclusion/exclusion criteria	Х	X														</t<>	Inclusion/exclusion criteria	Х	X													
Physical examination ² XX<	Height	Х														
Vital signs3XXX <t< td="">Body weight	Х				X			X			X			X	X	</t<>	Body weight	Х				X			X			X			X	X
Clinical laboratory tests (biochemistry, hematology, and urinalysis) ⁴ Serology testing (HIV, HCV and HBV [HBsAg, HBcAb or anti-HBc]) 12-lead ECG ⁵ X Y Pregnancy testing ⁶ X X X X X X X X X X X X X	Physical examination ²	Х	X	X	X	X	X	X	X	X	X	X	X	X	X	X
(biochemistry, hematology, and urinalysis)4XX Vital signs³	Х	X	х	X	Vital signs ³	Х	X	х	X	X	X	X	X	X	X	X	X	X	X	X
and HBV [HBsAg, HBcAb or anti-HBc])XImage: Second secon	Clinical laboratory tests (biochemistry, hematology, and urinalysis) ⁴	Х	x	x	x	x	x	X	X	X	X	X	X	x	x	x
Pregnancy testing ⁶ XXX	Serology testing (HIV, HCV and HBV [HBsAg, HBcAb or anti-HBc])	X														
TB evaluation ⁷ X X 12-lead ECG⁵	Х	X						X						X	X	12-lead ECG ⁵	Х	X						X						X	X
SALT assessment X Pregnancy testing⁶	Х	X	Pregnancy testing ⁶	Х	X	X	X	X	X	X	X	X	X	X	X	X	X	X
	TB evaluation ⁷	Х														
Medical photography ⁸ X X X X X X X X X X X X X X X X X X X	SALT assessment	Х	X	X	X	X	X	X	X	X	X	X	X	X	X	X
Medical photography ⁸ X X <t< td="">																</t<>																
	Medical photography8	Х	X	X	X	X	X	X	X	X	X	X	X	X	X	X
	Whole blood transcriptomics		X	x		x			X		X	X			x	x
DC flow cytometry X X X X X X X X X X X X X X	DC flow cytometry	Х	X	X		X			X		X	X			X	X
PBMCs X X X X X	PBMCs		X	X					Х		Х					

PRIVATE AND CONFIDENTIAL INFORMATION OF HORIZON THERAPEUTICS IRELAND DAC

Procedure Window (days)														
Serum biomarkers	X	X	X		X			X		X	X		X	X
Plasma biomarkers	X	x	X		X			X		x	X		X	X
Blood MxA		x	x		X			X		X	X		X	X
Daxdilimab serum PK testing ¹⁰		x x x x x x x x x x x												
Serum daxdilimab ADA ¹¹		X	x	X	X			X			X		X	X
Concomitant medication monitoring	Continuous													
Adverse event monitoring (AEs, SAEs, and/or AESIs)							Cor	ntinuous						

Abbreviations: ADA, anti-drug antibodies; AE, adverse event; AESI, adverse event of special interest; anti-HBc, antibody to hepatitis B core antigen; ALODEX, Alopecia Density and Extent; HBsAg, Hepatitis B surface antigen; ClinRO, Clinician Reported Outcome; DC, dendritic cell; ECG, electrocardiogram; EOT, end of treatment; ET, early termination; HBcAb, hepatitis B core antibody; HBV, hepatitis B virus; HCV, hepatitis C virus; HIV, human immunodeficiency virus; IFN, interferon; IP, investigational product; MxA, myoxvirus protein A; PBMCs, peripheral blood mononuclear cells; PK, pharmacokinetic; PPD, purified protein derivative; Q4W, every 4 weeks; SAE, serious adverse event; SALT, Severity of Alopecia Tool; SC, subcutaneous; TB, tuberculosis; Wk, week; WOCBP, women of childbearing potential.

¹ Participants who prematurely stop dosing will enter the post-treatment follow-up period of 16 weeks after the last dose received. Participants who do not enter the post-treatment follow-up period will be requested to complete the ET visit.

² A focused physical examination should be performed as described in Section 8.5.2.

³ Vital signs comprise heart rate, blood pressure, temperature, and respiratory rate. Vital signs will be performed pre-dose during the Treatment Period.

⁴ Laboratory tests will be performed pre-dose during the Treatment Period.

⁵ 12-lead ECG to be done pre-dose during the Treatment Period.

⁶ WOCBP (see Section 5.1 for definition) will have a serum pregnancy test at screening and urine pregnancy tests at other visits.

⁷ The results of an IFN-gamma release assay (ie, QuantiFERON-TB Gold performed within 12 weeks of the Screening visit (if available) are acceptable, provided there is no reason to suspect any re-exposure. If PPD is used, a second visit will be necessary for PPD reading only.

⁸ Medical photographs of the full scalp will be taken for all participants, and of the eyebrows and eyelashes for participants who have hair loss in these areas at baseline.

⁹ Participants will receive daxdilimability administered SC on Day 1 followed by All IP administrations will be done at the clinical site by the trial staff. On and and a participants will remain under observation for at least 1 hour after IP administration.

PRIVATE AND CONFIDENTIAL INFORMATION OF HORIZON THERAPEUTICS IRELAND DAC

¹⁰ Serum daxdilimab PK will be obtained on **Day 1** at the following timepoint: 2 hours (± 5 minutes) post-dose. Samples for PK will be obtained pre-dose on and any time during the trial visit on Weeks 36-48.

¹ Collection of blood samples for analysis of serum daxdilimab ADA must be performed prior to IP administration at all applicable visits.

¹² Local injection tolerability assessments including injection site reactions will be performed approximately 30 minutes post-injection (can be performed any time at a solution of the performed for any ongoing injection site reactions.

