1 PROTOCOL SUMMARY

1.1 Synopsis

Name of Sponsor/Company:	Name of Investigational Product:	Name of Active Ingredient:							
Horizon Therapeutics Ireland DAC	Daxdilimab (HZN-7734)	Daxdilimab (HZN-7734)							
Protocol Title:									
A Phase 2a, Open Label, Proof-of-Concept Trial of Daxdilimab for the Treatment of Moderate-to-Severe Alopecia Areata									
Phase of Development:									
Phase 2a									
Trial Center(s):									
This trial will be conducted at ap	proximately 8 sites located in Canada	and the United States.							
Number of Participants (plann	ed):								
The trial is planned to enroll app	roximately 30 participants with alopec	ia areata (AA).							
Duration of Trial:									
screening period, 32 weeks for daxdilimab mg	participant is approximately 52 weeks or the open-label treatment period w follow-up period.								
Investigational Product, Dosag	e, and Mode of Administration:								
Daxdilimab will be provided as	s a								
All participants will receive daxdilimab mg administered subcutaneously as two 1.5 mL injections All investigational product (IP) administration will be done at the clinical site by the trial staff. On and and participants will remain under observation for at least 1 hour after IP administration.									
Reference therapy, dosage and	mode of administration:								
Not applicable (N/A).									

Name of Sponsor/Company:	Name of Investigational Product:	Name of Active Ingredient:					
Horizon Therapeutics Ireland DAC	Daxdilimab (HZN-7734)	Daxdilimab (HZN-7734)					
Objectives and Endpoints:							
Primary Objective and Endpo	int						
Efficacy Objective	Efficacy Endpoint						
To evaluate the effect of daxdilimab on reducing hair loss at Week 24 in participants with AA.	ing hair score at Week 24.						
Secondary Objectives and End	lpoints						
Efficacy Objectives	Efficacy Endpoints						
To evaluate the effect of daxdilimab on reducing hair loss through 9 months of treatment in participants with AA.	SALT from baseline at Week	no achieve ≥50% reduction in					
To evaluate the post-treatment duration effect of daxdilimab on reducing hair loss in participants with AA.	 Percent change from baseline Weeks 40-48. Proportion of participants wh SALT from baseline at Week 	no achieve ≥50% reduction in					
	 Proportion of participants with absolute SALT score ≤ 10, 20, 30, 50 at Weeks 40-48. 						
Pharmacokinetic (PK)/ Pharmacodynamic (PD)/ Immunogenicity Objectives	PK/PD/Immunogenicity Endpoints	5					

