occur during the Week 24 visit. All participants will have a follow-up period of 16 weeks (through Week 48) to evaluate long-term safety and to observe the duration of efficacy following the treatment period. Participants who prematurely stop dosing will be followed through Week 48 unless participants withdraw consent of trial participation or are lost to follow-up. Any participant who discontinues from the trial prematurely and does not plan to participate in the post-treatment follow-up period will be requested to complete the early termination (ET) visit.

For scheduled trial visits, participants will come to the trial centers on 14 occasions: screening,

Efficacy will be evaluated by assessment of SALT scores,

Blood samples will be collected from all participants to characterize the PK, PD, and immunogenicity of daxdilimab.

Safety will be assessed by collecting AEs, SAEs, AESIs, performing local injection site tolerability assessment, recording vital signs, performing physical examinations and ECGs, and evaluating clinical laboratory results.

Inclusion/Exclusion Criteria:

Inclusion Criteria

All participants must meet all of the following criteria to be eligible for trial participation, either at the screening and Day 1 visits, or only at one of the specified visits (screening or Day 1) as noted in the criterion:

- 1. Written informed consent and any locally required authorization (eg, Health Insurance Portability and Accountability Act in the United States,) obtained from the participant prior to performing any protocol-related procedures, including screening evaluations.
- 2. Adult men and women, aged 18 to 65 years, inclusive, at the time of informed consent.
- 3. Willing and able to comply with the prescribed treatment protocol and evaluations for the duration of the trial.
- 4. Willing to keep the same hair style and color (eg, hair products, process, and timing for hair appointments) for the duration of the trial.
- 5. Clinical diagnosis of moderate-to-severe AA defined as the presence of ≥ 50% and ≤95% total scalp hair loss at screening and baseline (Day 1) defined by the SALT score.
- Duration of current episode of hair loss >3 months but <7 years at screening and Day 1, along with investigators' assessment that hair regrowth is possible. Total duration since diagnosis of AA could be >7 years.

Page 17 of 70

Name	of Sponsor/Company:	Name of Investigational Product:	Name of Active Ingredient:				

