4 TRIAL DESIGN

4.1 Overall Design

This is a Phase 2a, multicenter, open-label, proof-of-concept trial to assess the preliminary efficacy, safety, tolerability, PK, and PD of daxdilimab in participants with moderate-to-severe AA, with \geq 50% and \leq 95% total scalp hair loss as defined by the Severity of Alopecia Tool (SALT) score at Screening and Day 1. Participants will be between 18 and 65 years of age (inclusive), with a current episode of hair loss of >3 months but <7 years, along with investigator's assessment that hair regrowth is possible and no evidence of active regrowth present at baseline, and no known history of significant regrowth during the last 6 months. Approximately 30 participants will be enrolled to receive daxdilimab mg administered subcutaneously

All participants will read and sign an informed consent form (ICF) prior to any screening procedures being performed. Participants who meet all inclusion criteria and none of the exclusion criteria may be accepted into the trial.

The trial will comprise of a screening period of up to 30 days with enrollment on Day 1. Participants will be treated with daxdilimab mg mg matter the primary endpoint assessment will occur during the Week 24 visit. All participants will have a follow-up period of 16 weeks (through Week 48) to evaluate long-term safety and to observe the duration of efficacy following the treatment period. Participants who prematurely stop dosing will be followed through Week 48 unless participants withdraw consent of trial participation or are lost to follow-up. Any participant who discontinues from the trial prematurely and does not plan to participate in the post-treatment follow-up period will be requested to complete the ET visit.

For scheduled trial visits, participants will come to the trial centers on 14 occasions: screening,

Efficacy will be evaluated by	y assessment of SALT scores,	

Blood samples will be collected from all participants to characterize the PK, PD, and immunogenicity of daxdilimab.

Safety will be assessed by collecting AEs, SAEs, adverse events of special interest (AESIs), performing local injection tolerability assessment, recording vital signs, performing physical examinations and electrocardiograms (ECGs), and evaluating clinical laboratory results.

Page 34 of 70

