6 TREATMENT

6.1 Trial Treatment Administered

This trial involves SC administration of daxdilimab mg (two 1.5 mL injections) The IP will be administered by trial site staff in the clinic. On Day 1 and participants will remain under observation for at least 1 hour after IP administration. The IP will be provided by the sponsor. Further details regarding the IP can be found in Table 2.

Table 2: Trial Treatment

	Investigational Product
Product name	Daxdilimab
Dosage form	
Source of procurement	Horizon Therapeutics
Unit dose strength(s)/Dosage level(s)	mg dose, administered as 2 x 1.5 mL SC injections.
Route of Administration	Subcutaneous, (total of 9 doses)
Physical description	
Dosing instructions	Daxdilimab should be administered by clinic staff trained in best practices for SC administration of treatments. More details on the administration method are described in the study manual.
Abbreviations: ; SO	, subcutaneous.

The contents of the label will be in accordance with all applicable regulatory requirements.

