8.5.5 Local Injection Tolerability Assessments

Assessor local injection tolerability assessments will be performed approximately 30 minutes post-dose (can be performed any time at Week 36 as no IP is administered), at the visits specified in Table 1. The investigator, or designee, will evaluate the injection sites at these visits, and will document the presence or absence of local intolerance/injection site reactions and will open an AE in case of local injection site intolerance. Additional follow-up after Week 36 can be performed for any ongoing injection site reactions.

8.6Adverse Events and Serious Adverse Events

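### Table 1 footnote 1 and the rest of the plan disagree on how long early stoppers are followed, so SALT visits that the SAP analyses may go uncollected

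*Protocol*

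**What the plan says.** **The footnote.** Protocol Section 1.3, Table 1, footnote 1: "Participants who prematurely stop dosing will enter the post-treatment follow-up period of 16 weeks after the last dose received". This fixes both the length of follow-up and its starting point.

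**The other passages.**
- Synopsis: "Participants who prematurely stop dosing will be followed through Week 48 unless participants withdraw consent of trial participation or are lost to follow-up".
- Section 4.1: "Participants who prematurely stop dosing will be followed through Week 48", with the same exceptions.
- Section 7.1.1: participants permanently taken off the product continue with protocol assessments to Week 48, with the same two exceptions. Sites are to be trained on retention.
- Section 9.3.2.4 and SAP 4.7.1.3: early stoppers are asked to keep attending planned visits for the rest of the study, and their off-treatment data are analysed.

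**What the SAP analyses.** The primary endpoint is percent change in SALT at Week 24. The secondary SALT endpoints cover Weeks 12-36 and, for duration of effect after treatment, Weeks 40-48. Uncollected continuous values are filled by LOCF (Protocol 9.3.2.5; SAP 4.7.1.4 and 4.7.2.2). For binary endpoints, SAP 4.7.2.2 and 4.7.2.3 use LOCF for skipped visits and non-response after early dropout.

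**Completion.** Section 4.4 counts a participant as completing the trial on reaching either Week 48 or the early-termination (ET) visit. Sections 4.1 and 7.1 reserve the ET visit for people who leave prematurely. SAP 4.4 reports trial completion and trial discontinuation as separate lines.

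**The concern.** A site that works from the schedule table could stop seeing an early stopper 16 weeks after the last dose, while the analysis sections assume SALT is still being collected. Values never collected cannot be recovered. LOCF would fill the continuous endpoints, and the no-imputation sensitivity analysis in SAP 4.7.1.5 would simply have fewer participants.

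The Weeks 40-48 endpoints are the most exposed. They are meant to show whether an effect persists off treatment, and a value carried forward from an earlier visit says nothing about that.

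The conflict matters only for participants who stop dosing and stay in the trial. Those who withdraw consent or are lost to follow-up are excepted under the longer rule as well. For those who take a prohibited medication considered effective for AA, the main analyses already replace later values, so only the sensitivity analyses lose data after that use.

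Two further points:
1. If follow-up can properly end before Week 48, the SAP does not say whether the later visits are skipped (LOCF) or follow early dropout (non-response) for binary endpoints.
2. Independently of the footnote, the Section 4.4 definition would let someone who leaves prematurely and attends ET fit both disposition lines.

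**Working it through.** **The conflict needs no dosing interval.** Treatment lasts 32 weeks (synopsis: "screening period, 32 weeks for") and follow-up lasts 16 weeks and ends at Week 48 (Section 4.1). This gives 32 + 16 = 48, which reproduces the plan's own end point. For any last dose at week L < 32, the footnote ends follow-up at L + 16 < 48.

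**Visit counts need an inferred schedule.** The calendar is redacted. A 4-weekly schedule fits every visible figure:
- Doses at Weeks 0, 4, ..., 32 make 9; Table 2 gives a "total of 9 doses".
- Screening, Day 1 and Weeks 4, 8, ..., 48 make 1 + 1 + 12 = 14; Section 4.1 says "participants will come to the trial centers on 14 occasions".
- The last dose falls before Week 36; Section 8.5.5 says of the tolerability check that it "can be performed any time at Week 36 as no IP is administered".
- SAP 4.5 adds 28 days after the last dose when computing exposure.
- 30 days + 32 weeks + 16 weeks is about 52 weeks, the stated participation.

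The Table 1 row "SALT assessment" is marked in all 15 extracted columns (14 visits plus ET). The SAP therefore analyses 10 SALT visits: Weeks 12, 16, ..., 48.

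**Visits lost under the footnote** (visits with week > L + 16):

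| Last dose | Footnote ends | Lost of 10 | Weeks 12-20 | Week 24 | Weeks 28-36 | Weeks 40-48 |
|---|---|---|---|---|---|---|
| Day 1 | Week 16 | 8 | 1 | 1 | 3 | 3 |
| Week 4 | Week 20 | 7 | 0 | 1 | 3 | 3 |
| Week 8 | Week 24 | 6 | 0 | 0 | 3 | 3 |
| Week 12 | Week 28 | 5 | 0 | 0 | 2 | 3 |
| Week 16 | Week 32 | 4 | 0 | 0 | 1 | 3 |
| Week 20 | Week 36 | 3 | 0 | 0 | 0 | 3 |
| Week 24 | Week 40 | 2 | 0 | 0 | 0 | 2 |
| Week 28 | Week 44 | 1 | 0 | 0 | 0 | 1 |
| Week 32 | Week 48 | 0 | 0 | 0 | 0 | 0 |

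Over the eight early rows the losses total 36 visits, of which 21 (58%) fall in Weeks 40-48. That share gives each stopping time equal weight. It counts possible stopping times, not participants.

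**Length of carry-forward to Week 48:** 48 - (L + 16) = 32 - L weeks, from 4 weeks (L = 28) to 32 weeks (L = 0).

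**Effect on a mean.** With 30 participants, one carried value shifts that visit's mean by d/30, where d is the carried minus the uncollected value. For an assumed d of 10 to 50 percentage points: 10/30 = 0.3 and 50/30 = 1.7 points.

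**Effect on a binary rate.** If follow-up can end before Week 48, choosing LOCF or non-response moves a rate by at most 1/30 = 3.3 points per affected participant.

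**Number affected.** The documents give no early-stopping rate, so the total effect cannot be computed.

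**The case against.** **A softer reading.** The footnote may only name the period that early stoppers enter, which other sections describe as running through Week 48. The column headings of Table 1 are not legible, so the footnote's anchor cannot be seen. But its wording counts 16 weeks from the last dose, and for an early stopper that does not reach Week 48. The softer reading does not remove the conflict.

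**Five passages against one.** Section 7.1.1 is the operative section on discontinuation and adds retention training, so some sites may follow the longer rule anyway. Nothing shows that a visit will in fact be lost. This stands as a limit on likelihood. However, sites work from the schedule table, and no statement of precedence is visible.

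**Small effect.** Protocol Table 6 implies a standard error near 7.8 points, hence a 95% half-width of about 1.96 x 7.8 = 15 points. One participant at the top of the assumed range moves the mean by 1.7/15, about 11% of that. The trial is single-arm and descriptive, with no decision rule. This stands too: the concern is mainly about the secondary duration endpoints.

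**The further points.** The binary-endpoint gap disappears if follow-up always runs to Week 48. The completion definition would need attention even without the footnote, and SAP 4.4 does not say that it uses that definition, so double counting is possible rather than certain. Both are fair, and both points are kept within those bounds.

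**Conclusion.** The contradiction is real and can be read directly from the current text. It holds for any last dose before Week 32, whatever the dosing interval.

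Under the inferred 4-weekly schedule, following the footnote would leave 1 to 8 of the 10 analysed SALT visits uncollected for a participant who stops early but stays in the trial. Every early stopping time loses at least Week 48, and a last dose at Week 20 or earlier loses all of Weeks 40-48. The primary endpoint is touched only by a last dose at Day 1 or Week 4.

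The effect per participant is modest, and the number of participants is unknown. The point should be fixed because the lost data cannot be recovered and the repair is cheap, not because a conclusion of the trial is at risk.

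**What to change.** - Reconcile Table 1 footnote 1 with the synopsis, Protocol Sections 4.1, 7.1.1 and 9.3.2.4, and SAP 4.7.1.3, so that a single end of follow-up for participants who stop dosing early is stated everywhere. Which rule applies is for the sponsor to settle. Then confirm that the SALT visits to be collected and those the SAP analyses are the same.
- Only if the reconciled follow-up can end before Week 48, add a sentence to SAP 4.7.2.2 and 4.7.2.3 saying whether LOCF or non-response applies to the later scheduled visits.
- Align the Section 4.4 completion definition with the reconciled rule and with SAP 4.4, so that a participant who leaves prematurely and attends ET is not also counted as a completer.

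The cost is wording wherever the passages disagree, one definition, a memo to sites and, conditionally, one SAP sentence. Any extra visits would be ones that other sections already plan.
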